#### 2) Data Review Committee

This is an open-label trial, and in order to ensure objectivity in efficacy assessment, a DRC will be established as a third-party organization to assess the safety and efficacy at each dose based on a consistent perspective of specialists. The DRC will separately specify their procedures to be followed.

#### 3) Treatment Period

For mild and moderate CDI, American College of Gastroenterology (ACG) 2013 guideline recommends a 10-day administration of VCM or MTZ. A 10-day comparison study between 400 mg/day fidaxomicin (hereafter, FDX) and 500 mg/day VCM confirmed that FDX has a clinical therapeutic effect for CDI comparable to VCM, and FDX is approved to treat CDI with the regimen of twice daily for 10 days. In reference to these, we selected 10 days for the treatment period.

The treatment period for enteric infection is usually 3 to 7 days, although it differs according to the causative pathogen, improvement of clinical symptoms, and type of antimicrobial drug. For an exploratory assessment on how OPS-2071 affects clinical response and microbiological outcome, the trial adopts a 7-day treatment period, regardless of the causative pathogen or the efficacy during the trial so as to confirm the safety and usefulness of OPS-2071.

In the result of the 7-day multiple dose study on OPS-2071 in healthy male adults, some intestinal bacteria decreased because of the repeated administration of OPS-2071.

Protocol No. 341-13-002

However, regardless of the dose of OPS-2071, the intestinal bacterial flora returned to the baseline status by the time of follow-up after the end of treatment. There was no apparent effect on intestinal bacterial flora.

#### 4) Follow-up 2 (CDI group)

The problem in the treatment for CDI is its high recurrence rate. CDI responds to the treatment with MTZ or VCM but recurs in approximately 15% to 30% cases. CDI repeatedly recurs, which may result in hospitalization and treatment for a long period. In this trial, for exploratory confirmation of the effect of OPS-2071 to prevent recurrence, presence/absence of recurrence will be confirmed 28 days after the end of treatment (FU2: Day 38) or at withdrawal in patients who achieved "clinical cure" at the end of treatment in the CDI group.

# 3.3 Endpoints

# 3.3.1 Safety Endpoints

Adverse events, clinical laboratory tests, vital signs (body temperature, blood pressure, and pulse rate), 12-lead ECG

# 3.3.2 Efficacy Endpoints

# 3.3.2.1 Microbiological Outcome

Microbiological outcome will be judged according to the assessment criteria shown in Table 3.3-1 and Table 3.3-2 for the bacterial strain isolated as the causative pathogen based on the data from the microbiological examination. For infection due to multiple causative pathogens, microbiological outcome will be assessed for each individual pathogen.

 Table 3.3-1
 Assessment Table for Microbiological Outcome

	Assessment of				
Baseline	Day 4	End of Treatment	Microbiological Outcome		
+	-	_	Excellent		
+	1				
_	+	_	Good		
+	Not applicable				
+	1				
_	+	,	Poor		
+	_	+			
+	Not applicable				
	Others		Unknown/ indeterminate		

+: culture positive, -: culture negative

Not applicable: Bacterial culture test was not performed. The causative pathogen was not isolated or identified.

Table 3.3-2 Assessment Criteria for Microbiological Outcome

Assessment of Microbiological Outcome	Definition			
Excellent	Pathogen is absent from bacterial culture obtained at Day 4 and at the end of treatment.			
Good	Pathogen is still present in bacterial culture obtained at Day 4, and absent from bacterial culture at the end of treatment.			
Poor	Pathogen is still present in bacterial culture obtained at the end of treatment.			
Unknown/indeterminate	Applicable to none of the above but falls under the cases below for example.     Cultures are not available because of withdrawal from the study or other reasons.			
	Culture was obtained after the use of prohibited concomitant drugs/therapies.			
	Any other circumstance, which makes it impossible to define the microbiological response.			

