## 3.4 Target Number of Patients

A total of 60 patients with 20 patients (10 patients each in CDI and enteric infection groups) in each dosing group

Enroll 10 patients in each dosing group of the CDI group to assess microbiological outcome. For the enteric infection group, enroll at least five patients in each dosing group to assess microbiological outcome with the sum of *Salmonella*, *Campylobacter*, and pathogenic *E. coli*. If a sufficient number of patients are not available for microbiological assessment after enrollment of 10 patients in each group, enroll more patients.

Patients available for microbiological assessment are those assessed as either "excellent," "good," or "poor" according to Table 3.3-2, which means that patients assessed as "Unknown/indeterminate" will not be included in microbiological assessment.

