#### 9.2 Criteria and Procedures for Withdrawal of Individual Patients

In any of the events listed below, the investigator or subinvestigator will discontinue IMP administration, perform the tests to be performed at withdrawal stipulated in Section 7.1, Schedule and Procedures of the Trial, and promptly inform the sponsor of the withdrawal (Annex, Emergency Contact). The investigator or subinvestigator will record the date and reason for withdrawal in the source documents and CRF.

If withdrawal is necessitated by problems with safety, such as the occurrence of an AE or aggravation of the underlying disease, the investigator or subinvestigator will promptly take appropriate measures and perform follow-up if necessary (refer to Section 8.4 Follow-up Investigation of Adverse Events).

- 1. If the patient wishes to withdraw
- 2. If it is found after the start of the trial that the patient did not meet all the inclusion criteria or fell under any of the exclusion criteria
- 3. If a drug or therapy from either item 1 or item 7 in the list of prohibited concomitant drugs and therapies is used or judged to be required
- 4. If an AE making continuation of trial participation difficult occurs
- 5. If the female patient is found to be pregnant
- 6. If symptoms of the primary disease exacerbate, and the investigator or subinvestigator judges that it is not appropriate to continue the trial participation
- 7. If it becomes impossible to comply with the protocol for any another reason or if the investigator or subinvestigator judges that it is necessary to discontinue the trial participation for any another reason

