# 11.1.3 Microbiological per Protocol Set

The microbiological per protocol set (MPPS) comprises those patients in the FAS for whom the causative pathogen is identified and for whom microbiological outcome is assessed as "Excellent", "Good", or "Poor" according to the Assessment Criteria of Microbiological Outcome (Table 3.3-2), excluding patients for whom microbiological outcome is assessed as "Unknown/indeterminate".

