**MPPS** 

3) Analysis Method

Analysis will be performed by disease group and by dose, and by MIC values of OPS-2071 against the causative strain. The number and proportion of patients by causative strain, a list of causative strain by patient, and a list of the result based on bacterial culture at each evaluation time point will be prepared.

Concerning microbiological outcome by causative strain, bacteria elimination rate and its 95% CI will be calculated. The bacteria elimination rate is the proportion of causative strains assessed as either "excellent" or "good" except for those assessed as "Unknown/indeterminate". In case of infection of multiple bacteria, assess the microbiological outcome of each infections agent.

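### Failures can be coded Unknown and dropped from the only planned elimination rate, which probably biases it upward

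*Protocol*

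**What the plan says.** **Coding.** Protocol 3.3.2.1, Table 3.3-2 gives Unknown/indeterminate as a residual category with examples. Two matter here: "Cultures are not available because of withdrawal from the study or other reasons" and "Culture was obtained after the use of prohibited concomitant drugs/therapies". Table 3.3-1 reads cultures at baseline, Day 4 and end of treatment only; every other pattern is Unknown.

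**Withdrawal.** Two withdrawal criteria in section 9.2 matter. Criterion 3 reads: "If a drug or therapy from either item 1 or item 7 in the list of prohibited concomitant drugs and therapies is used". It also covers the case where such treatment is only thought necessary. Criterion 6 reads: "If symptoms of the primary disease exacerbate, and the investigator or subinvestigator judges that it is not appropriate to continue the trial participation". Item 1 is antibacterials in the enteric infection group. Item 7 is other therapy for CDI or enteric infection in both groups.

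**Analysis.** Section 11.1.3 defines MPPS as patients rated Excellent, Good or Poor, "excluding patients for whom microbiological outcome is assessed as" Unknown/indeterminate. Section 11.3.4.1 analyses elimination in MPPS only: "The bacteria elimination rate is the proportion of causative strains assessed as either" Excellent or Good, again without the Unknowns. Section 11.2 rules out imputation. The full analysis set (FAS) is defined, but no efficacy endpoint is analysed in it.

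**Enrolment.** Section 3.4 does not count Unknowns as available for microbiological assessment and adds: "If a sufficient number of patients are not available for microbiological assessment after enrollment of 10 patients in each group, enroll more patients". The assessable targets per dose are 10 in the CDI group and at least 5 in the enteric group.

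**Clinical response.** Section 3.3.2.3, Table 3.3-3 rates a patient who received therapy for the infection before the observation as a clinical failure.

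**The concern.** Membership of MPPS depends on what happens after dosing starts. A patient whose infection persists and who is given another treatment, or who leaves before the last culture, can disappear from the numerator and the denominator of the elimination rate. That patient is a clinical failure in one table and absent from the other.

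Microbiological outcome is the first-listed efficacy endpoint. It sets the enrolment target (11.5) and is meant to inform the next phase (1.2.3). Efficacy at 100 mg also decides which doses follow (3.1). With 10 or 5 assessable patients per dose and disease group, one or two omitted failures change how a dose looks. If failures differ between doses, the distortion can differ too.

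**Working it through.** **1. The plan's own figure.** Section 11.5 assumes detection of almost 100% in CDI and 50% in enteric infection.
- CDI: 10 / 1.00 = 10. Enteric: 5 / 0.50 = 10. Three doses × (10 + 10) = 60, as stated.
- There is no allowance for Unknowns. If a share u of patients with a detected pathogen becomes Unknown (assumed 10%, 20%, 30%), the chance that all of the first 10 CDI patients are assessable is (1 − u)^10 = 35%, 11%, 3%. Expected enrolment to reach 10 is 10 / (1 − u) = 11.1, 12.5, 14.3.
- In the CDI group any Unknown among the first 10 triggers more enrolment. In the enteric group only fewer than 5 assessable of 10 does. On the protocol's 50% detection alone, the chance of at least 5 is 62.3%, so top-up there has a 37.7% chance even with no Unknowns.

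**2. The same patient under each rule**

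| Course | Microbiological outcome | Clinical response |
|---|---|---|
| Given other therapy for the infection, cultured afterwards | Listed under Unknown; left out | Failure |
| Withdrawn, no culture | Unknown; left out | Assessed at withdrawal if during dosing |
| Withdrawn during dosing, culture positive at withdrawal | Not mapped in Table 3.3-1 | Assessed at withdrawal |

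**3. Expected size.** Let p be the true elimination rate, f the share of failures coded Unknown and g the share of successes coded Unknown, with one causative strain per patient.

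Reported rate = p(1 − g) / [p(1 − g) + (1 − p)(1 − f)]

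The documents give neither f nor g, so all values are assumptions.

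| f | g | True 70% | True 80% |
|---|---|---|---|
| 25% | 0 | 0.70/0.925 = 75.7% | 84.2% |
| 50% | 0 | 0.70/0.85 = 82.4% | 88.9% |
| 75% | 0 | 0.70/0.775 = 90.3% | 94.1% |
| 50% | 10% | 0.63/0.78 = 80.8% | 87.8% |
| 50% | 25% | 0.525/0.675 = 77.8% | 85.7% |
| 30% | 30% | 70.0% | 80.0% |

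The bias is upward whenever f exceeds g, and zero when they are equal.

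**4. In counts** (exact 95% intervals), when omitted failures are put back:
- CDI, 8/10 = 80.0% (44.4–97.5). With one: 8/11 = 72.7% (39.0–94.0). With two: 8/12 = 66.7% (34.9–90.1). With three: 8/13 = 61.5% (31.6–86.1).
- Enteric, 4/5 = 80.0% (28.4–99.5). With one: 4/6 = 66.7% (22.3–95.7). With two: 4/7 = 57.1% (18.4–90.1). With three: 4/8 = 50.0% (15.7–84.3).

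**5. Does the bias grow with the number of failures?** Take f = 2/3 and g = 0. The bias is 3p/(1 + 2p) − p: 17.5 points at p = 0.70, about 26.8 at p = 0.37 and 15.0 at p = 0.10. It rises and then falls, so the worst dose does not necessarily gain most.

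**The case against.** The strongest reply is that the text does not force failures into Unknown. The category applies only when no other does, and a positive end-of-treatment culture meets the definition of Poor. A stool culture is scheduled at withdrawal: always in the CDI group (7.1.7.1), and during dosing in the enteric group (7.1.7.2). Section 7.2.2.1 lists withdrawal as a time point for this endpoint. Criterion 3 also applies when another drug is merely judged to be required, so a culture before that drug is possible. If a positive withdrawal culture counts as Poor, many failures stay in the rate. This stands, and it limits the claim. It does not remove the problem, because the protocol never says how that culture is classified. Read literally, the residual wording could even let a negative end-of-treatment culture after other therapy count as Excellent or Good, which also raises the rate.

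Successes can become Unknown too, through missed stools or prohibited drugs taken for other reasons, and that shrinks the bias.

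A reader might infer more than the documents support:
- *Every lost failure is replaced.* That describes the CDI group only until 10 are assessable; enteric top-up starts only below 5 of 10.
- *The loss is invisible.* Baseline characteristics are tabulated by dose for both FAS and MPPS (11.3.2), so the gap can be seen, though not the reasons for it.
- *The MPPS rate decides the dose path.* The Data Review Committee judges safety and efficacy under separately specified procedures (3.2), and clinical response counts the same treated patients as failures.
- *The bias is largest where failures are most frequent.* Step 5 of the working shows otherwise.

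Finally, the sample size is not statistically derived, no test rests on this rate, and its intervals are descriptive.

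**Conclusion.** The concern holds as a probable upward bias of unknown size in the only planned elimination rate. Exclusion of Unknowns and their omission from the assessable target are explicit. The direction rests on one inference: that withdrawal criteria 3 and 6 make failures likelier than successes to become Unknown. For a true 70%, the illustrative range is 75.7% to 90.3% when 25% to 75% of failures and no successes are lost; it is 70% if loss is unrelated to outcome. How far the scheduled withdrawal culture limits the bias cannot be settled, because it is not mapped. The conflict with the clinical response rule does not depend on any assumption. In a descriptive phase 2a trial this should be fixed; it does not invalidate the trial.

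**What to change.** 1. **Tables 3.3-1 and 3.3-2.** State that a culture at withdrawal during the treatment period serves as the end-of-treatment culture when there is none, so that a positive one is Poor.
2. **Section 11.3.4.1.** Add an elimination rate over all treated patients with a causative pathogen identified under Table 3.3-1, keeping its rows for a negative baseline and a positive Day 4. Count as not eliminated any patient given other therapy for the study infection before the end-of-treatment culture, whatever a later culture shows. In a sensitivity analysis, also count withdrawal for lack of effect without a culture as not eliminated; this stays out of the added rate itself because it infers culture status from symptoms.
3. **Reporting.** Show this rate beside the MPPS rate, with Unknowns by reason and dose, and state how many patients were enrolled as top-up under 3.4 and 11.5.

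Two shortcuts should be avoided. Day 38 cultures must not define Poor, because that would turn elimination at end of treatment into recurrence. A positive Day 4 culture alone must not define Poor after an unrelated withdrawal, because Day 4 positive followed by negative is rated Good.

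The cost is wording and one extra table. The cultures and therapy records are already collected. The downside is a lower reported elimination rate.

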# 3.3.2.2 Toxin A/B Assay (Clostridium Difficile Infection Group Only)

Assess positive or negative for toxin A/B.

# 3.3.2.3 Clinical Response

The investigator or subinvestigator will refer to the information from patients (eg, patient diary), and assess clinical response at the time of observation (Day 4 and end of treatment) according to the assessment criteria shown in Table 3.3-3.

Table 3.3-3 Assessment Criteria for Clinical Response

Clinical Response Assessment	Definition
Clinical cure	Meeting all the following criteria within 24 hours before observation  No liquid or unformed stool
	No abdominal symptoms and no other symptoms (fever, nausea, vomiting)
	No need of medication or therapy to treat CDI or enteric infection
Clinical improvement	Fulfilling at least one of the following criteria within 24 hours before observation  • Liquid or unformed stools ≤ 2 times/day
	No abdominal symptoms and no other symptoms (fever, nausea, vomiting)
	No need of medication or therapy to treat CDI or enteric infection
Clinical failure	Fulfilling none of the above-mentioned clinical improvement criteria.  Patients who received medication or therapy to treat CDI or enteric infection prior to the time of observation are to be assessed as "clinical failure".

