**CPPS** 

3) Analysis Method

Analysis will be performed by disease group and by dose, by causative strain, and by MIC values of OPS-2071 against the causative strain. Calculate frequency distribution at each evaluation time point and prepare a list of causative strains by patients.

Calculate the clinical response rate and 95% CI at each evaluation time point. Clinical response rate will be calculated as the proportion of the patients judged as "clinical cure" or "clinical improvement" against evaluable patients except for those with missing data.

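### Clinical improvement can be met solely by being judged not to need therapy, so the clinical response rate can count patients whose stools and symptoms have not changed

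*Protocol*

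**What the plan says.** Section 3.3.2.3, Table 3.3-3 (same text in the synopsis), defines three categories, assessed by the investigator at Day 4 and at end of treatment.

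- Cure requires all of: no unformed stool, no symptoms, no need of therapy.
- Improvement requires "Fulfilling at least one of the following criteria within 24 hours before observation". The criteria are "Liquid or unformed stools ≤ 2 times/day"; freedom from abdominal symptoms, fever, nausea and vomiting; and "No need of medication or therapy to treat CDI or enteric infection".
- Failure is "Fulfilling none of the above-mentioned clinical improvement criteria". A further sentence adds: "Patients who received medication or therapy to treat CDI or enteric infection prior to the time of observation are to be assessed as" clinical failure.

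Section 11.3.4.3 then states: "Clinical response rate will be calculated as the proportion of the patients judged as" cure or improvement, among evaluable patients in the clinical per protocol set (CPPS), with a 95% CI. It also asks for the frequency distribution of the categories at each time point.

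**The concern.** The three criteria are alternatives, and one of them describes neither stools nor symptoms. A patient who still has the stool frequency and symptoms of entry is classed as improved if the investigator judges that no treatment for CDI or enteric infection is needed and none has been given. None of the criteria asks for a change from baseline. The CDI entry criteria (Section 5.2, item 6) require a stool count and a positive test but no abdominal symptom, fever, nausea or vomiting, so some CDI patients may meet the symptom criterion before the first dose as well.

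This matters because efficacy is a primary objective (Section 2), and Sections 1.2.3 and 3.1 name only two efficacy measures in describing what the trial assesses: microbiological outcome and clinical response. If the response rate mainly records the absence of a judged need for therapy, it says little about differences between doses.

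**Working it through.** **Stated figures.** The protocol gives no expected response rate and no expected rate of need for therapy, so there is no such figure to reproduce. The target of 10 per dose and disease group is consistent with the total: 3 × (10 + 10) = 60 (Section 3.4). Section 11.5 says this number was not chosen by statistical methods.

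**Logic of the table.** With three yes/no criteria there are 2³ = 8 patterns. At least one criterion is met in 7 of them; all three are met in 1. Before the received-therapy sentence is applied, 7 of 8 patterns are a response. The only failing pattern has more than 2 unformed stools, symptoms present and therapy judged necessary. Receipt of therapy turns any pattern into failure.

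**Floor.** Let p1 be the share with 2 or fewer unformed stools, p2 the share free of symptoms, and p3 the share who neither need nor receive therapy. Everyone counted in p3 is a responder, so the response rate is at least p3, whatever p1 and p2 are.

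**Numbers (all assumed).** Take p1 = p2 = 0.2, meaning little clinical effect. If the criteria are nested, the any-one rate is max(p1, p2, p3) = p3. If they are independent, it is 1 − (1 − p1)(1 − p2)(1 − p3). That formula ignores the override for patients who received therapy; applying it moves the rate down towards p3.

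| p3 | Any one: nested | Any one: independent | Stool and no need: p1·p3 | All three: p1·p2·p3 |
|---|---|---|---|---|
| 0.95 | 95% | 96.8% | 19% | 3.8% |
| 0.90 | 90% | 93.6% | 18% | 3.6% |
| 0.80 | 80% | 87.2% | 16% | 3.2% |
| 0.70 | 70% | 80.8% | 14% | 2.8% |
| 0.50 | 50% | 68.0% | 10% | 2.0% |

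The last two columns assume independence; under nesting neither can exceed 20%.

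**Sensitivity to a real clinical difference.** Raise p1 from 0.2 to 0.7 and p2 from 0.2 to 0.6, holding p3 = 0.9. The any-one rate goes from 93.6% to 1 − 0.3 × 0.4 × 0.1 = 98.8%, a gain of 5.2 points. Stool and no need together go from 18% to 0.7 × 0.9 = 63%. All three go from 3.6% to 0.7 × 0.6 × 0.9 = 37.8%. At p3 = 0.5 the any-one rate does move more, from 68.0% to 94.0%. An active dose would probably raise p3 too, so these contrasts isolate stools and symptoms only.

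**Ten-patient illustration (assumed).** Three are cured; five have 3 or more unformed stools and symptoms but have received no therapy; two received therapy. If k of the five are judged not to need therapy, the rate is (3 + k)/10.

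- k = 0: 3/10 = 30% (exact 95% CI 6.7% to 65.2%).
- k = 5: 8/10 = 80% (44.4% to 97.5%).

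Stools and symptoms are identical in both cases. Only the judgement of need differs.

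**The case against.** The strongest reply is that need is not the same as receipt. The end-of-treatment visit falls on the day after the last dose (Section 3.1.1), and an investigator facing a patient with persistent diarrhoea, pain and vomiting may well judge that treatment is needed. That patient meets none of the criteria and is a failure. An inactive dose can therefore produce failures. This stands. A reader might infer that the response rate is close to 100% by definition at any dose, or that anyone merely not yet put on another drug counts as improved; the table supports neither. But the reply also concedes that the classification then turns on the investigator's view of need in an open-label trial.

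A reader might also see a contradiction for a patient with 2 unformed stools who received therapy. There is none: the received-therapy sentence settles it as failure.

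It is tempting to say that failures leave the denominator, because Section 9.2, item 3 withdraws patients in whom the listed prohibited therapy is used or judged required, and Section 11.3.4.3 leaves out missing data. In the illustration with k = 5, that would turn 8/10 into 8/8 = 100% (exact lower limit 0.025^(1/8) = 63.1%). The documents do not say this. Sections 7.1.7.1 and 7.1.7.2 require a response assessment at withdrawal during dosing, and the CPPS can keep these patients (Section 11.1.4). What remains open is whether that assessment counts at the end-of-treatment time point.

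There are real mitigations. Cure requires every criterion, the category frequencies are tabulated, recurrence is assessed only in cured patients, microbiological outcome is a separate endpoint, and the trial is small and descriptive. They let a careful reader see past the response rate, but they do not repair the rate and CI that the plan reports.

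**Conclusion.** The point holds in this form: under Table 3.3-3 and Section 11.3.4.3, every patient who neither needs nor receives CDI or enteric therapy is a responder regardless of stools or symptoms, so the response rate has that share as its floor. How high the floor is cannot be known from the protocol; over an assumed range of 0.5 to 0.95 it is 50% to 95%, while few of the same patients would meet stricter rules if stools and symptoms had hardly changed. The rate is therefore a weak basis for comparing doses.

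A reader might go further and infer that the definition would steer the Data Review Committee's effective or not-effective decision at 100 mg. That is a risk only. Section 3.2 leaves the committee's procedures to a separate specification, and nothing in the protocol ties its decision to this rate. The conclusion rests on reading the table as written; the percentages rest on assumed inputs.

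**What to change.** In Table 3.3-3 and the synopsis, stop the no-need criterion from being sufficient alone. Make it a necessary condition for improvement together with 2 or fewer unformed stools per day, with or without the symptom criterion. Requiring all three is the strictest version: improvement would then differ from cure only by allowing one or two unformed stools, and a patient with formed stools but residual nausea would be a failure. That choice should be made openly. Define failure as every assessed patient who meets neither cure nor improvement, or who received CDI or enteric therapy.

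In Section 11.3.4.3, report the clinical cure rate with its 95% CI beside the response rate, and state that response assessments made at withdrawal during dosing count in the end-of-treatment rate.

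The cost is a wording change to one table, the synopsis and one analysis section. No new data are needed, although the diary alone is not enough: it holds stools and symptoms (Section 7.2.2.6), receipt of therapy comes from the concomitant-treatment records (Section 6.2), and need comes from the investigator's assessment (Section 7.2.2.3). The downside is a lower reported response rate.
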